## PURPOSE SAP

### Protocol # B1801035

- The follow-up time for patients who had malignancies will be censored at the diagnosis date for each type of malignancy. The follow-up time after diagnosis of a malignancy will not be included in the calculation of time at risk or not at risk for the same type of malignancy. However, patients who reported a malignancy are still at risk of having a different type of malignancy. Malignancy types include but are not limited to: Solid malignant tumors, Non-melanoma skin cancers, Malignant tumors of hemopoietic and lymphoid tissues, Carcinoma in-situ.
- Time at risk (in years; for the current/recent etanercept-treated group only) of serious or pre-specified opportunistic infection (excluding malignancies) and other SAEs (excluding serious or pre-specified opportunistic infection and malignancies), respectively: cumulative period of etanercept exposure defined as the sum of each etanercept treatment period,  $[\text{date of last dose} - \text{date of first dose} + 1 + 28]/365.25$ .
- Time not at risk (this applies to time in years accrued after discontinuation of etanercept while followed in the registry, and excludes malignancies) of serious or pre-specified opportunistic infection and other SAEs, respectively: cumulative period without current/recent use of etanercept  $\{[(\text{date of study discontinuation}) - (\text{date of last dose} + 28) + 1] + [\text{intervals between treatment periods} > 28 \text{ days}]\}/365.25$ . For analysis purposes, time not at risk is the total study follow-up time minus the time at risk, which is defined above.
- Incidence rate is calculated as the number of individual events observed during the time at risk, divided by the total number of patient-years at risk for the event, multiplied by 100. Please note that the time at risk for malignancy will be censored at the diagnosis date of that specific malignancy.

In the example below, all person-time in blue would contribute to the ‘current/recent’ category, while all person-time in yellow would contribute to the ‘past treatment’ category for the assessment of SAEs and serious or opportunistic infections. Patients would be considered at risk of malignancies in both the blue and yellow periods.

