4.2. Inclusion Criteria

To be eligible for registry enrolment, patients must meet all of the following criteria:

- Age ≤ 17 years at time of administration of the first dose of etanercept
- Diagnosis of plaque psoriasis by a dermatologist
- Prior to enrolment, a clinical decision has been made to prescribe etanercept for the treatment of psoriasis
- Newly prescribed with initial etanercept or actively being treated with etanercept, regardless of length of treatment prior to study enrolment
- Capable and willing to provide paediatric assent, or written informed consent when applicable, and
- Parent(s)/legal representative of patient is capable and willing to provide written informed consent

- Evidence of a personally signed and dated informed consent document indicating that the patient (or a legally acceptable representative) has been informed of all pertinent aspects of the study must exist.

Please note: Currently etanercept is approved for the treatment of severe plaque psoriasis in children and adolescents from the age of 6 years who are inadequately controlled by, or are intolerant to, other systemic therapies or phototherapies. The registry protocol will not encourage use of etanercept at younger ages. However if a doctor, in collaboration with the child's parents, makes the independent clinical decision to prescribe etanercept to a child less than 6 years of age for severe plaque psoriasis, that child may be included in the registry.

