## **PURPOSE SAP**

**Protocol # B1801035**

Any patient who receives at least one dose of etanercept will be included in the evaluation for safety. The primary focus of this Registry is safety; however, to the extent possible effectiveness (or lack of effectiveness) will be inferred from patterns of treatment and re-treatment. In addition, the change of severity of plaque psoriasis as a measure of effectiveness will also be assessed, if these data are available among the majority of patients.

Primary analyses will be limited to prospective data, i.e., events reported during participation in the registry. Serious and pre-specified opportunistic infections and malignancies reported as part of retrospective data collection will be included in a summary of medical history and co-morbid conditions.

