## **6.3 Methods for withdrawals, missing data, and outliers**

Patients may withdraw consent at any time. If a patient withdraws prior to completing the Registry follow-up period, any reason for withdrawal is to be documented. All information already collected as part of the Registry will be retained for analysis.

Several attempts will be made to contact patients and to limit missing data. In general, there will be no imputation of missing data. Data will be presented and summarized as they were recorded. However, in estimating the person-time at risk for inclusion in the sum of current/recent etanercept use, missing start or stop date of adverse events or etanercept treatment will be handled as follows:

- (1) If the day element of the start date of the most recent period of etanercept exposure is missing, it will be assumed to be the 15th of the month.
- (2) If the day element of the start date of a serious/pre-specified opportunistic infection or other SAE is missing, it will be assumed to be the 15th of the month.
- (3) If the last dose of the most recent period of etanercept exposure prior to onset of a serious/pre-specified opportunistic infection or other SAE is recorded as unknown, the reporter is asked to indicate whether it was known to be within the 28 days prior to event onset. The time at risk will be estimated to be the larger of the following: (a) time between the start date of the most recent period of etanercept exposure prior to the onset of AE and the AE onset date, and (b) 29 or (1 + 28) days.
- (4) If the month element of the event or treatment are missing, it will be assumed to be the mid of the year, i.e., July 1st.

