#### **6.4 Populations for analysis**

The population for analysis includes all enrolled patients who are documented as having received at least one dose of etanercept. No internal comparator group is included in the Registry; however, where applicable, external data sources such as geographically appropriate (country-specific) population-based incidence rates (age and gender-specific) of malignancy and tuberculosis (TB) may be used to generate standardized incidence ratios (SIRs) to aid interpretation of incidence rates of malignancies and tuberculosis estimated based on data from the registry. Due to the small sample size and expected rarity of the events, this approach may be of limited value.

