#### **6.5 Planned subgroups**

Descriptive analyses will be stratified, where specified, by:

- Enrollment type: Prospective (i.e., patients who started etanercept within 30 days before the enrollment date or any time after enrollment date) or retrospective
- Treatment period (initial 24 weeks/post 24 weeks/all follow-up)
- Completion of initial 24 weeks of etanercept exposure (yes/no/unknown)

Analysis of outcomes of interest:

- Etanercept exposure status (current/recent or past)
- Infection status (none during follow-up/in association with recent or current exposure/in association with past exposure)

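### Infection and other-SAE time at risk is not started at enrolment, so read literally it counts event-free pre-enrolment treatment of patients already on etanercept

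*SAP*

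**What the plan says.** **Time at risk.** For infections and other SAEs, SAP 6.6 uses the "cumulative period of etanercept exposure defined as the sum of each etanercept treatment period", each period contributing last dose minus first dose, plus 1, plus 28 days. Protocol 7.4 uses the same course-plus-28-days idea. Neither mentions the enrolment date. By contrast, malignancy time in both documents has a stated start (first dose) and end (diagnosis or end of follow-up).

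**Past time.** SAP 6.6 describes it as "time in years accrued after discontinuation of etanercept while followed in the registry" and gives an explicit formula. It then sets the working rule: "For analysis purposes, time not at risk is the total study follow-up time minus the time at risk, which is defined above".

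**Unknown last dose.** When the last dose before an event is unknown, rule (3) of SAP 6.3 takes the larger of 29 days and the "time between the start date of the most recent period of etanercept exposure prior to the onset of AE and the AE onset date". Enrolment is again not mentioned.

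**Who is included.** Protocol 4.2 admits patients "actively being treated with etanercept, regardless of length of treatment prior to study enrolment". Protocol Table 0-1 and section 6.2.1 have their earlier dosing abstracted from records. SAP 6.4 states: "The population for analysis includes all enrolled patients who are documented as having received at least one dose of etanercept". SAP 7 bases tables on the total registry population unless otherwise specified, and the infection analyses in SAP 7.3 set no narrower population.

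**Which events count.** SAP 4, like Protocol 7.1, states: "Primary analyses will be limited to prospective data, i.e., events reported during participation in the registry". Infections found retrospectively are summarised separately.

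**The concern.** The numerator and denominator of the current/recent rate are bounded differently. Events count only from enrolment, but as written person-time counts from the first dose of each treatment period, even when that dose came before enrolment. For a patient already on treatment, the time between first dose and enrolment cannot contribute a primary-analysis event, yet it enlarges the denominator.

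The subtraction rule then takes this pre-enrolment time away from in-registry follow-up. That inflates the past-treatment rate and can make an individual's past time negative. Both effects push the current/recent versus past rate ratio down.

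The current/recent rate is the estimate for the registry's first objective, so the error would make infection risk on treatment look lower than observed. Protocol 7.6 already warns that depletion of susceptible patients may dilute risk in this group. The mechanism here is different but acts in the same direction.

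**Working it through.** The documents give no person-time or rate for this point, so there is no planned figure to reproduce. As a check on the reading, a single dose gives 0 + 1 + 28 = 29 days under SAP 6.6, which matches the 29 days in rule (3) of SAP 6.3.

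**One patient (illustrative).** 1.5 years of use before enrolment, then 3.5 years on drug within 5 years of follow-up. 28 days = 28/365.25 = 0.08 years.
- Current/recent, literal: 1.5 + 3.5 + 0.08 = 5.08 years. Observed in the registry: 3.5 + 0.08 = 3.58 years.
- Past, by subtraction: 5 - 5.08 = -0.08 years. Observed: 5 - 3.58 = 1.42 years.
- Past, by the explicit formula in the same bullet: 5 - (3.5 + 28/365.25) + 1/365.25 = 1.43 years. Past time therefore shrinks only under the subtraction rule, which is the one SAP 6.6 says to use.

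**Rule (3) of SAP 6.3.** A course started 1.5 years before enrolment with an event 1 year after enrolment counts 1.5 + 1.0 = 2.5 years at risk, against 1.0 year observed.

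**Cohort.** The share of already-treated patients and their prior exposure are not given; Protocol 6.2 expects their number to be limited. Assumptions: 70 patients (middle of the 60 to 80 target in Protocol 3 and SAP 4), 4.5 years of follow-up and 2 years on drug after enrolment, ignoring the 28-day tails. Then current/recent time PT1 = 70 x 2 = 140 patient-years (PY) and past time PT2 = 70 x 2.5 = 175 PY. Added time E = 70 x share x prior years. The rate is multiplied by PT1/(PT1 + E), and the ratio by that factor times (PT2 - E)/PT2.

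| Share | Prior use (y) | E (PY) | Rate x | Ratio x |
|---|---|---|---|---|
| 5% | 0.5 | 1.75 | 140/141.75 = 0.988 | 0.978 |
| 5% | 1.5 | 5.25 | 140/145.25 = 0.964 | 0.935 |
| 10% | 0.5 | 3.5 | 140/143.5 = 0.976 | 0.956 |
| 10% | 1.5 | 10.5 | 140/150.5 = 0.930 | 0.874 |

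The number of patients cancels from the multipliers, so the larger target of 100 to 200 in SAP 6.2 would not change them. Time on drug does matter: with E = 10.5 and 1, 2 or 3 years on drug, the rate multiplier is 70/80.5 = 0.870, 0.930 or 210/220.5 = 0.952. A 5% fall in the rate needs 140/0.95 - 140 = 7.4 PY of pre-enrolment time.

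**Restricting to prospective patients.** SAP 6.5 defines these as "patients who started etanercept within 30 days before the enrollment date or any time after enrollment date", so up to 30 days each could still enter. The extreme, with all 70 at 30 days, is 70 x 30/365.25 = 5.75 PY, giving 140/145.75 = 0.961.

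**Will the ratio be calculated?** SAP 7.3 requires at least 5 infections in each exposure group. Protocol 1.1 reports three severe infections in a 211-patient trial. Assuming 36 to 48 weeks of exposure each, that is 145.6 to 194.1 PY, or 2.06 to 1.55 per 100 PY. At equal rates on and off drug, the expected counts in 140 and 175 PY are 2.89 and 3.61, or 2.16 and 2.70. The Poisson probability of at least 5 in both groups is about 0.05 to 0.01.

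**The case against.** The best defence is that in-registry time was plainly intended. Subtracting time at risk from study follow-up makes sense only if the first lies within the second. The past-time bullet speaks of time while followed in the registry, and SAP 7.2 runs its exposure summary from enrolment to end of follow-up. SAP 6.6 also relies on a coloured example figure that is not available here, and the table shells are not available either; any of these may show the limit. This stands as evidence of intent. A reader might infer that the analysis was programmed with pre-enrolment time, or that a reported rate is biased; the documents do not show that. They show only that no available written formula sets the limit.

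A second defence is that SAP 6.6 defines incidence as events observed during the time at risk, which ties numerator to denominator. It does not close the gap. If time at risk reaches back before enrolment, SAP 4 and Protocol 7.1 still exclude the events from that time.

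A third is size. With 3 events the exact Poisson 95% interval runs from about 0.2 to 2.9 times the estimate, far wider than a shift of 1% to 7%. That is true, but a known downward error in a safety rate should not be left in because the estimate is imprecise.

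A reader might also infer an equally serious fault at the end of follow-up, because the added 28 days are not capped. The documents do not support that. The reporting period in Protocol 9 extends to 28 days after the last dose, so this tail is mostly observed time. If half of 70 patients were on drug at exit and the tail were wholly unobserved, it would be 35 x 28/365.25 = 2.7 PY, or 1.5% of past time.

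**Conclusion.** The point holds for the enrolment start. As written, SAP 6.6 and rule (3) of SAP 6.3 let event-free pre-enrolment time into the current/recent denominator, and the working rule for past time removes it a second time, with negative values possible for an individual. Protocol 7.4 shares the definition and does not supply the missing limit.

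The likely size is modest: a current/recent rate multiplied by about 0.99 to 0.93 under the assumed 5% to 10% of already-treated patients, 0.5 to 1.5 years of prior use and 2 years on drug. The true share and prior exposure are unknown. With no pre-enrolment exposure the error does not arise. A reader might infer a seriously distorted rate ratio, but that ratio will probably not be calculated, and the registry is descriptive with no hypothesis test at stake. The uncapped tail and the mismatch between the two past-time formulas are minor. The point should be fixed because the stated rule gives a wrong safety rate for patients the protocol expressly admits. Confidence is medium, since the missing figure may already show the intended limit.

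**What to change.** In SAP 6.6, define one observation window per patient:
- **Start:** the later of enrolment and first dose.
- **End:** the end of the AE reporting period in Protocol 9 or, if earlier, death, last contact for a patient lost to follow-up, or withdrawal of consent for further data.
- **Current/recent time:** days in the window covered by any course from first dose to last dose plus 28 days.
- **Past time:** all remaining days in the window, so that neither quantity is negative and the two sum to follow-up.

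Apply the same window to rule (3) of SAP 6.3, delete the explicit past-time formula, and state that the Protocol 7.4 definition is read the same way. Report pre-enrolment events and person-time only in the separate retrospective summary. If the example figure already shows this limit, put it into words beside the formula.

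The cost is one derivation and one imputation rule, using dates already collected. The reported current/recent rate may become slightly less favourable.

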### **5.3 Definition and measurement of exposure/risk windows**

#### **5.3.1 Etanercept**

##### **TREATMENT PERIODS (INITIAL AND SUBSEQUENT)**

It is anticipated that the etanercept treatment status for each patient will change throughout follow-up. A standard course of etanercept treatment is expected to last up to 24 weeks. Patients successfully responding to the first etanercept treatment course may be exposed to subsequent treatment (i.e., when patients experience a disease flare) and time window between 2 (or more) consecutive courses of treatment may vary substantially.

For the initial course of etanercept, whether the patient completed 24 weeks of treatment is recorded (yes/no), and if no, the number of weeks of treatment will be reported. Completion of initial 24 weeks of etanercept is defined as starting the first dose of etanercept within 30 day before the enrolment date or any time after enrolment date, and continuing for at least 168 days.

For each subsequent treatment period of etanercept, start and stop dates of treatment are collected. For all subsequent periods, the duration of treatment in weeks will be calculated. Cumulative exposure will be calculated by the sum, for each etanercept treatment period, of: [last dose date – first dose date] + 28. If there are less than 28 days between treatment periods, exposure will be considered uninterrupted (i.e., part of the same treatment period).

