##### **CURRENT/RECENT TREATMENT VERSUS PAST TREATMENT**

In order to interpret reported events, time at risk of occurrence is established based on current or recent (within 28 days) exposure and past exposure.

**Past exposure** is defined as any exposure to etanercept, at any dose, with no reported exposure within the last 28 days.

**Current/recent exposure** is defined as on active etanercept treatment at the time of the event, or last dose of treatment within 28 days (inclusive) preceding the event.

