#### **6.6 Derivations**

The following derived/calculated values will be used:

[figure not shown]
- Age at enrollment in years:  $[\text{date of enrollment} - \text{date of birth} + 1] / 365.25$
- Duration of disease at enrollment in years:  $[\text{date of enrollment} - \text{date of diagnosis} + 1] / 365.25$
- Cumulative exposure in weeks by the duration of chronic exposure for each period of etanercept exposure:  $[(\text{last dose date} - \text{first dose date} + 1) + 28] / 7$ . A treatment period is defined as continuous treatment with no interruptions of more than 28 days. Restarting treatment within 28 days is considered as having continuous exposure
- Duration of each etanercept treatment period (in weeks):  $(\text{last dose date} - \text{first dose date} + 1) / 7$
- Time at risk of malignancy (in years):  $[\text{date of malignancy diagnosis or end of follow-up if no malignancy is found} - \text{initial treatment dose date} + 1] / 365.25$

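### SAP 6.6 gives two rules for time not at risk that disagree: the explicit formula recounts 28-day tails, and the residual rule beside it does not cut time at risk at the limits of observation

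*SAP*

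**What the plan says.** SAP section 6.6 defines time at risk of infection and of other SAEs as "cumulative period of etanercept exposure defined as the sum of each etanercept treatment period". Each period contributes last dose minus first dose, plus 1, plus 28 days.

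The next bullet covers time not at risk, described as "cumulative period without current/recent use of etanercept". Its formula has two parts:

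- study discontinuation minus (last dose + 28), plus 1;
- the "intervals between treatment periods" that exceed 28 days.

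The same bullet then adds: "For analysis purposes, time not at risk is the total study follow-up time minus the time at risk, which is defined above".

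Three other statements bear on where a period ends:

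- SAP 6.6: "A treatment period is defined as continuous treatment with no interruptions of more than 28 days". The duration of a period there runs from first to last dose, and the 28 days are added separately for cumulative exposure.
- SAP 5.3.1: "If there are less than 28 days between treatment periods, exposure will be considered uninterrupted".
- SAP 5.3.1 defines past exposure as any exposure "with no reported exposure within the last 28 days".

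SAP 7.3 uses the two quantities as PT1 (current/recent) and PT2 (past) in the incidence rate ratio (IRR), which is calculated only with at least 5 infections in each group. The incidence rate stratified by current/recent and past exposure has no such threshold. The SAP gives no formula for total study follow-up.

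**The concern.** Every course carries its 28-day tail into time at risk. If a treatment period ends at the last dose, the interval up to the next course still contains that tail, and the explicit formula adds the interval whole. The closing +1 also counts the day last dose + 28 again. The formula therefore cannot equal follow-up minus time at risk, although the bullet presents both as the same quantity.

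PT2 is the denominator of the past rate and a multiplier in the IRR. A programmer and a validator who each follow a different half of the bullet would get different past rates and ratios for the registry's first objective. Repeat courses are expected (Protocol 2.1.2 and 7.4, SAP 5.3.1), and the discrepancy grows with each one.

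**Working it through.** **Notation.** Course i runs from first dose F_i to last dose L_i, with k courses and discontinuation on day D. Follow-up is FU = D - F_1 + 1. Starting at first dose and counting both end days are assumptions.

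**Time at risk (SAP 6.6).** AR = sum of (L_i - F_i + 29).

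**Time not at risk, explicit formula.** NR = (D - L_k - 28 + 1) + sum of (F_{i+1} - L_i - 1), taking an interval as its dose-free days, each longer than 28.

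**Sum.** The dose dates telescope, so AR + NR = D - F_1 + 28k - 26. Subtracting FU leaves 28k - 27 = 28(k-1) + 1 excess days per patient. The residual rule leaves 0.

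**Numbers.** FU = 1826 days (5 years, Protocol section 5). Courses last 168 days (24 weeks, SAP 5.3.1), so each adds 196 days to AR. Gaps of 84 days are assumed; 40-day gaps give the same excess for k = 2 and 5.

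| k | AR | Residual | Explicit formula | Excess | Ratio |
|---|---|---|---|---|---|
| 1 | 196 | 1630 | 1631 | 1 | 1.001 |
| 2 | 392 | 1434 | 1463 | 29 | 1.020 |
| 3 | 588 | 1238 | 1295 | 57 | 1.046 |
| 5 | 980 | 846 | 959 | 113 | 1.134 |

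For k = 2 the second course ends on day 420, so the formula gives (1826 - 448 + 1) + 84 = 1463. A count of calendar days reproduces the residual column exactly.

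**Shorter follow-up.** Courses on days 0-161 and 222-383 with exit on day 700: AR = 190 + 190 = 380; formula (700 - 411 + 1) + 60 = 350; residual 701 - 380 = 321. The excess is again 29 days, now 350/321 - 1 = 9%.

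**Effect on the ratio.** IRR = (a/PT1)/(b/PT2) = (a × PT2)/(b × PT1), so it rises by the ratio column if all patients share that pattern. The past rate falls by the same factor.

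**Other readings of the interval.** A plain date difference F_{i+1} - L_i gives 29(k-1)+1 days. An interval that starts after the tail gives 1 day for any k.

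**Residual rule at exit.** One course on days 1-1820 with exit on day 1826: AR = 1820 + 28 = 1848, so the residual is 1826 - 1848 = -22 days. The day count gives 1826 current/recent and 0 past.

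The error need not show as a negative value. With courses on days 1-168 and 253-1820, AR = 196 + 1596 = 1792 and the residual is 34. The true past days are 197 to 252, which is 56, so 22 days have moved from PT2 to PT1. This pushes the IRR down, opposite to the formula's error.

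**Residual rule at entry.** Time at risk starts at first dose. SAP 6.5 lets even prospective patients start up to 30 days before enrolment, and retrospective patients earlier. If follow-up starts at enrolment, subtraction removes treated days that it never contained.

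**The case against.** The strongest reply is that the sentence after the formula opens by saying what applies for analysis. It is most naturally read as taking precedence, and under it PT1 and PT2 sum to follow-up by construction. That stands. A reader might infer from the formula that the analysed denominators overlap and exceed follow-up; the documents do not support that unless the formula is what gets programmed.

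A second reply is that the time-at-risk bullet places the 28 days inside each period, so the intervals could begin after the tail. That reading is possible but weaker. SAP 6.6 computes period duration to the last dose, and SAP 5.3.1 compares the gap between periods with 28 days. If the longer-than-28-days condition were applied after the tail, dose-free gaps of 29 to 56 days would lose their past time. The one-day overlap would remain in any case. The drawing for the coloured person-time example in SAP 6.6 was not in the text available to me, so I rely on it for neither side.

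Third, the consequence is modest. SAP 5.2.5 expects some treatment to be continuous, and such a patient contributes 1 day. The IRR has its five-event threshold and no hypothesis test is planned. With 5 infections in each group and equal person-time, the SAP 7.3 interval runs from about 0.23 to 4.35, so a shift of a few percent would not change the interpretation. That stands too, although the stratified rates have no threshold.

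On the residual rule, Protocol section 9 extends adverse event reporting to 28 days after the last dose when that is later than exit. If follow-up were defined to include that extension, the -22 would become 0. The SAP does not say so, and its own formula ends at study discontinuation.

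**Conclusion.** The point holds as an inconsistency in the SAP. Two definitions of one denominator stand in one bullet and differ by 28(k-1)+1 days per patient, on the better supported reading that a period ends at the last dose. The analysed denominators are wrong from this cause only if the explicit formula is used. Then the past rate is too low and the IRR too high by about 2% with two 24-week courses over 5 years and about 13% with five, and by more with shorter follow-up.

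These are per-pattern figures. The documents give neither the number of courses per patient nor the total past patient-years, so no cohort-wide percentage can be claimed.

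Keeping only the residual rule is not enough. With follow-up ending at discontinuation, or starting at enrolment after the first dose, it misallocates time and can turn negative.

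**What to change.** Delete the explicit formula and replace the bullet with a day-by-day rule:

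- The observed window runs from the later of first dose and enrolment to the end of observation.
- A day in the window is current/recent if it falls between the first dose and last dose + 28 of any course, and past otherwise. Each day is counted once, and tails are cut at both ends of the window.
- State whether the end of observation is study discontinuation or the end of the Protocol section 9 reporting period, and count infections over the same window.

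Program a check that PT1 + PT2 equals observed time for every patient and that neither is negative. The check does not replace the truncation: the 34-against-56-day case above passes it.

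If a closed formula is wanted, the past time is [end - (last dose + 28)] plus, for each gap, its dose-free days minus 28. The first term must be set to zero when negative, and time at risk must be cut by the same amount.

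The cost is one SAP bullet and one program check, with no new data.
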